11.1.4 Non-target lesions

All lesions (or sites of disease) not identified as target lesions, including pathological lymph nodes and all non-measurable lesions, should be identified as non-target lesions and be recorded at baseline.

Measurements of these lesions are not required and they should be followed as ‘present’, ‘absent’ or in rare cases, ‘unequivocal progression’.

11.2 Evaluation of response criteria

11.2.1 Target lesions

Complete Response (CR):	Disappearance of all target lesions
Partial Response (PR):	At least a 30% decrease in the sum of the longest diameter (LD) of target lesions, taking as reference the baseline sum LD
Progressive Disease (PD):	At least a 20% increase in the sum of the LD of target lesions, taking as reference the smallest sum LD recorded since the treatment started or the appearance of one or more new lesions
Stable Disease (SD):	Neither sufficient shrinkage to qualify for PR nor sufficient increase to qualify for PD, taking as reference the smallest sum LD since the treatment started

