3 OBJECTIVES

3.1 Primary Objective

Phase I - Confirm DLT:

The phase I portion of the study is a dose escalation to confirm the safety of the combination and to determine the DLT and the RP2D for ribociclib with Tamoxifen.

Phase Ib Dose Expansion:

Our goal is to further evaluate their safety in adult patients with ER+/HER2- locally advanced or metastatic breast cancer. Phase I trials are increasingly including dose-expansion cohorts after the maximum-tolerated dose (MTD) has been reached to better characterize the toxicity profile or identify early signs of efficacy within a specific disease population. We will evaluate two cohorts in the phase I expansion. The first will be the standard 21 days of ribociclib dosing with 7 days rest period and the second will be the continuous dosing (daily). Tamoxifen, per SOC, will be dosed daily in both cohorts. We will attempt to assess the anti-tumor activity ribociclib + Tamoxifen.

3.2 Secondary Objectives:

- Time to progression
- Overall survival from study initiation at 6 months, 12 months, 18 months and 24 months.
- Pre-treatment and post-treatment ER receptor expression in tumor in those patients who volunteer for optional tissue evaluation.
- **Pharmacokinetics** in the dose escalation as well as the dose expansion arms.

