4 INCLUSION CRITERIA

A. Shared Eligibility

1. Histologically and/or cytologically confirmed diagnosis of ER+ and/or PR+ breast cancer by local laboratory.
2. HER2-negative breast cancer defined as a negative in situ hybridization test or an IHC status of 0, 1+ or 2+. If IHC is 2+, a negative in situ hybridization (FISH, CISH, or SISH) test is required by local laboratory testing.
3. Patients are allowed (but not required) to have up to **two** lines of prior chemotherapy regimens in the metastatic setting for the dose expansion phase (). For the dose escalation cohort, up to three previous lines of chemotherapy in the metastatic setting is acceptable.
4. Measurable disease, i.e., at least one measurable lesion as per RECIST 1.1 criteria only **for expansion cohorts**.

5. For **escalation cohorts**, bone only disease is allowed. For expansion cohorts, there must be measurable disease as stated above (#4)..
6. ECOG PS 0 or 1.
7. Written informed consent must be obtained prior to any screening procedures and according to local guidelines.
8. Patient has adequate bone marrow and organ function as defined by the following laboratory values:
 - a. Absolute neutrophil count $\geq 1.5 \times 10^9/L$.
 - b. Platelets $\geq 100 \times 10^9/L$.
 - c. Hemoglobin $\geq 9 \text{ g/dL}$.
 - d. Potassium, total calcium (corrected for serum albumin), magnesium, and sodium within normal limits for the institution or corrected to within normal limits with supplements before first dose of study medication
 - e. INR ≤ 1.5 .
 - f. Serum creatinine $\leq 1.5 \times \text{ULN}$ or creatinine clearance $\geq 50 \text{ mL/min}$
 - g. In the absence of liver metastases, alanine aminotransferase (ALT) and aspartate aminotransferase (AST) $< 2.5 \times \text{ULN}$. If the patient has liver metastases, ALT and AST $< 5 \times \text{ULN}$.
 - h. Total bilirubin $\leq \text{ULN}$; or total bilirubin $\leq 3.0 \times \text{ULN}$ or direct bilirubin in patients with well-documented Gilbert's Syndrome
9. Must be able to swallow ribociclib and Tamoxifen capsules/tablets

B. Pre-menopausal Women Eligibility

1. Premenopausal women who received adjuvant Aromatase Inhibitor and Ovarian Suppression (AI + OS) in the adjuvant setting and completed at least 12 months of hormonal therapy.
2. Pre-menopausal women with *de novo* metastatic disease are eligible if they have had no prior endocrine therapy.

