8.7 Treatment Duration

Eligible patients will receive treatment as described above, in consecutive 4-week cycles, until progression of disease or unacceptable toxicity. Patients are expected to receive treatment for at least 2 cycles, at which time the first evaluation for efficacy will occur. If there is continued safety and tolerability in the absence of any documented disease progression, treatment may continue for 2 years or until progression or non-tolerance.

Patients will be followed for evaluation of safety for at least 30 days after the last dose of study drug. Any study drug-related serious adverse events will be followed until resolution, return to baseline grade, or deemed irreversible by the Investigator.

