11.1 Criteria for Target Lesions

11.1.1 *Measurable disease*

Measurable lesions are defined as those that can be accurately measured in at least one dimension (longest diameter to be recorded) as ≥ 20 mm with conventional techniques (CT, MRI, x-ray) or as ≥ 10 mm with spiral CT scan. All tumor measurements must be recorded in millimeters (or decimal fractions of centimeters).

11.1.2. *Non-measurable disease*

All other lesions (or sites of disease), including small lesions (longest diameter < 20 mm with conventional techniques or < 10 mm using spiral CT scan), are considered non-measurable disease. Bone lesions, leptomeningeal disease, ascites, pleural/pericardial effusions, lymphangitis cutis/pulmonis, inflammatory breast disease, abdominal masses (not followed by CT or MRI), and cystic lesions are all non-measurable.

11.1.3. *Target lesions*

- All measurable lesions up to a **maximum of two lesions per organ** and **five lesions in total**, representative of all involved organs, should be identified as target lesions and recorded and measured at baseline.
- Target lesions should be selected on the basis of their size (lesions with the longest diameter) and be representative of all involved organs, as well as their suitability for reproducible repeated measurements.
- All measurements should be recorded in metric notation using calipers if clinically assessed. A **sum of the diameters (longest for non-nodal lesions, short axis for nodal lesions)** for all target lesions will be calculated and reported as the baseline sum diameters, which will be used as reference to further characterize any objective tumor regression in the measurable dimension of the disease. If lymph nodes are to be included in the sum, only the short axis will contribute.

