11.4.2 Conventional CT and MRI

Conventional CT and MRI should be performed with cuts of 10 mm or less in slice thickness contiguously. Spiral CT should be performed using a 5 mm contiguous reconstruction algorithm. This applies to the chest, abdomen, and pelvis.

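### Section 11.2.1 defines target-lesion progression as a 20% rise with no minimum absolute increase, and nothing says whether it or the named RECIST 1.1 standard governs

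*Combined protocol and SAP*

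**What the plan says.** Section 11.2.1 writes out target-lesion progression as "At least a 20% increase in the sum of the LD of target lesions". The comparison is with the lowest sum seen on treatment, and a new lesion also counts as progression. No section adds a minimum increase in millimetres.

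Three provisions allow a very small target sum. In the expansion cohorts Section 4 asks for "at least one measurable lesion as per RECIST 1.1 criteria only". Section 11.1.1 accepts a lesion "as ≥ 10 mm with spiral CT scan". Section 11.1.3 caps the number of target lesions but requires no more than one.

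Confirmation by a repeat scan at least four weeks later is required for CR and PR (Sections 8.6 and 11). No such requirement is stated for progression.

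Progression has three uses. Treatment runs "in consecutive 4-week cycles, until progression of disease or unacceptable toxicity" (Section 8.7; Section 10.1 is similar). Section 3.2 lists "Time to progression" as a secondary objective. Section 11.3 takes best overall response only over the period before progression.

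Sections 8.6, 10.1 and 11 also name RECIST 1.1 as the basis for judging response or progression. The documents do not say what applies if that standard and the rule in Section 11.2.1 differ.

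**The concern.** The rule is purely relative and its reference is the lowest sum yet recorded. For a small sum, the required increase is a millimetre or two. One low reading also lowers the bar for every later scan. With no confirmation step, a single high reading after a low one is enough.

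A false call would end the patient's time to progression early and stop any later response from counting. It would also meet the treatment-continuation condition in Sections 8.7 and 10.1. Because the governing definition is not settled, two readers following the same protocol could classify the same small change differently.

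**Working it through.** No sample size, alpha or power figure in the plan depends on this rule, so there is no stated figure to reproduce. The check is threshold arithmetic followed by an illustrative simulation.

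**Threshold.** Required increase = 0.20 × smallest sum.

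| Smallest sum (mm) | Increase that meets the rule (mm) |
|---|---|
| 10 | 2 |
| 15 | 3 |
| 20 | 4 |
| 25 | 5 |
| 30 | 6 |
| 50 | 10 |

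The 20% applies to the sum. A 2 mm change is therefore enough only when the smallest sum is 10 mm or less, as with a sole 10 mm target lesion.

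**Inputs to the illustration.** The 20% threshold and the nadir reference come from Section 11.2.1, and the 10 mm minimum from Section 11.1.1. Section 8.6 sets scans every 8 weeks for the first 12 months: 52 / 8 = 6.5, so six scans. The reading error is an assumption: independent normal errors with a fixed SD of 0.5, 1.0 or 1.5 mm. True size does not change.

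**First follow-up scan, single lesion of true size d.** The false-progression probability is P(Y1 ≥ 1.2 × Y0) = 1 − Φ(0.2d / (SD × √(1 + 1.2²))), where √2.44 = 1.562. For d = 10 mm:
- SD 0.5: 2 / 0.781 = 2.56, giving 0.5%
- SD 1.0: 2 / 1.562 = 1.28, giving 10%
- SD 1.5: 2 / 2.343 = 0.85, giving 20%

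**Any of six scans, with the running minimum as reference (200,000 simulated patients).** The last column adds a 5 mm minimum increase, for illustration only.

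| True target sum | SD per lesion (mm) | 20% rule alone | 20% and 5 mm |
|---|---|---|---|
| one lesion, 10 mm | 0.5 | 8% | about 0% |
| one lesion, 10 mm | 1.0 | 70% | 0.4% |
| one lesion, 10 mm | 1.5 | 90% | 13% |
| one lesion, 15 mm | 1.0 | 31% | 0.4% |
| one lesion, 20 mm | 1.0 | 8% | 0.4% |
| one lesion, 30 mm | 1.0 | 0.1% | 0.1% |
| two lesions, 10 mm each | 1.0 | 37% | 9% |

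A 5 mm minimum stops mattering once the smallest sum reaches 5 / 0.20 = 25 mm, because 20% of the sum is then already 5 mm.

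**Dependence on the error model.** If the error is instead proportional to diameter, the rule and the error scale together and size drops out. With a CV of 5%, 10% or 15%, a single 50 mm lesion gives the same 8%, 70% and 90% as a 10 mm lesion, and a 5 mm minimum changes nothing there. Concentration of the problem in small sums therefore rests on the fixed-millimetre assumption.

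**The case against.** The strongest reply is that the protocol names its standard: Section 10.1 ties treatment continuation to progression as RECIST v1.1 defines it, and Sections 8.6 and 11 adopt the same criteria. If that standard carries an absolute minimum, the gap may be only in the transcription. This stands in part. The content of the standard cannot be checked from the documents, and the appendix cited in Section 8.6 does not appear in the text reviewed. A reader might infer that Section 11.2.1 departs from RECIST 1.1, but the documents alone do not show this. They do show a written rule beside a named standard, with no order of precedence. Section 11.2.1 also needs aligning with Section 11.1.3, which uses the short axis for nodal lesions where 11.2.1 speaks only of longest diameter.

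The second reply concerns size, and it stands. A sole 10 mm target lesion is the least favourable case. Section 11.1.3 takes measurable lesions up to five and favours large ones that can be measured reproducibly. Section 8.6 asks for one radiologist per patient where possible and for a consistent technique, which may make errors less independent than assumed. Nothing indicates how many of the 40 patients would have small sums.

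Three stronger readings are tempting and should be resisted.
- Section 11.4.2 says "Spiral CT should be performed using a 5 mm contiguous reconstruction algorithm", and a reader might infer that any change below 5 mm is noise. Slice thickness is not the error of an in-plane diameter, so it is context only.
- A reader might cite a lesion that shrinks from 10 to 7 mm and is called progressive at 8.4 mm as a lost response. That 30% fall already meets the PR measurement criterion, subject to confirmation.
- A reader might infer that the test of 8 responses in 40 is compromised. It counts responses and is touched only where an early progression call pre-empts a later one. No effect on its stated error rate or power is shown.

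**Conclusion.** The point holds as a defect in an endpoint definition that should be corrected. The written rule can call a 2 mm reading difference progression, no confirmation is required, and the document does not say whether this rule or the named standard governs. The outcomes exposed are time to progression and, less directly, best response. The primary safety, DLT and RP2D objectives do not depend on it.

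The size is uncertain. With fixed, independent reading errors the false-progression risk is serious for a single lesion near 10 mm if the SD is 1 mm or more, modest if it is 0.5 mm, and negligible for a 30 mm lesion at SD 1 mm. These percentages are not a forecast for the trial.

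**What to change.** Reconcile the progression rule in Section 11.2.1 with the RECIST 1.1 standard named in Sections 8.6, 10.1 and 11. State that one definition governs both endpoint classification and the treatment-continuation provisions in Sections 8.7 and 10.1. For endpoint classification, write out alongside the 20% rule whatever absolute minimum increase the governing standard sets. The 5 mm column above only shows what such a minimum can do. It is not a recommended value, and no rule for stopping treatment is proposed here. Leave the new-lesion and non-target progression rules as they are.

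The cost is a sentence or two of text, with no added scans, visits or readers. The downside is that true progression in a very small lesion may be called one scan later.

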11.2.2 Evaluation of non-target lesions

Complete Response (CR):	Disappearance of all non-target lesions and normalization of tumor marker level
Incomplete Response/ Stable Disease (SD):	Persistence of one or more non-target lesion(s) and/or maintenance of tumor marker level above the normal limits

Progressive Disease (PD): Appearance of one or more new lesions and/or unequivocal progression of existing non-target lesions

11.3 Evaluation of Best Overall Response

The best overall response is the best response recorded from the start of the treatment until disease progression/recurrence (taking as reference for progressive disease the smallest measurements recorded since the treatment started). In general, the patient's best response assignment will depend on the achievement of both measurement and confirmation criteria.

Note:

- Patients with a global deterioration of health status requiring discontinuation of treatment without objective evidence of disease progression at that time should be reported as "symptomatic deterioration". Every effort should be made to document the objective progression even after discontinuation of treatment.
- The best overall response for an early death, i.e., a patient who dies without documentation of disease progression and before it was time to conduct the first tumor reassessment, will be considered unevaluable or not assessed adequately. Response will also be considered unevaluable for any patient receiving treatment (regardless of how much was received) who did not have any follow-up assessment completed before initiation of alternative treatment. These patients must be replaced in both the phase I portion and the phase Ib expansion.
- In some circumstances, it may be difficult to distinguish residual disease from normal tissue. When the evaluation of complete response depends upon this determination, it is recommended that the residual lesion be imaged by PET scan or be investigated by fine needle aspirate/biopsy before confirming the complete response status.

Target Lesions	Non-target Lesions	New Lesions	Overall Response
CR	CR	No	CR
CR	Non-CR/Non-PD	No	PR
PR	Non-PD	No	PR
SD	Non-PD	No	SD
PD	Any	Yes or No	PD
Any	PD	Yes or No	PD
Any	Any	Yes	PD

11.4 Guidelines for Evaluation of Measurable Disease

The same method of assessment and same technique should be used to characterize each identified and reported lesion at baseline and during follow-up. Imaging based evaluation is preferred to evaluation by clinical examination when both methods have been used to assess antitumor effect of a treatment.

11.4.1 Clinical Lesions

Clinical lesions will only be considered measurable when they are superficial (e.g., skin nodules, palpable lymph nodes). For the case of skin lesions, documentation by color photography including a ruler to estimate the size of the lesion is recommended. If measured by calipers, measurements have to be confirmed by two independent health care professionals.

11.4.2 Conventional CT and MRI

Conventional CT and MRI should be performed with cuts of 10 mm or less in slice thickness contiguously. Spiral CT should be performed using a 5 mm contiguous reconstruction algorithm. This applies to the chest, abdomen, and pelvis.

11.5 Confirmation Measurement/Duration of Response

11.5.1 Duration of Overall Response

The duration of overall response is measured from the time measurement criteria are met for CR/PR (whichever is first recorded) until the first date that recurrent or progressive disease is objectively documented (taking as reference for progressive disease the smallest measurements recorded since the treatment started).

The duration of overall complete response is measured from the time measurement criteria are first met for CR until the first date that recurrent disease is objectively documented.

11.5.2 Duration of Stable Disease

Stable disease is measured from the start of the treatment until the criteria for progression are reached, taking as reference the smallest measurements recorded since the treatment started.

11.6 Evaluable disease

Patients must have measurable disease for dose expansion phase. Patients with bone only disease for this protocol are eligible if at least one lesion can be measured by MRI that is measurable by RECIST 1.1. Tumor markers are not considered measurable.

12 ADVERSE EVENT REPORTING

Investigators are required by Federal Regulations to report serious adverse events. This study will utilize the Common Toxicity Criteria version 4.03 to determine the severity of the reaction for adverse event reporting.

A serious adverse event is any adverse drug experience occurring at any dose that:

1. results in death;
2. is life-threatening;
3. results in in-patient hospitalization or prolongation of existing hospitalization (admissions for elective surgeries or procedure do not qualify);
4. results in a persistent or significant disability/incapacity; or
5. results in congenital anomaly/birth defect.

Reporting requirements and procedures depend upon: (1) whether agents are suspected of causing the adverse event, (2) whether the possibility of such an adverse event was reported in the protocol, consent form, or manufacturer's literature (expected or unexpected adverse event), (3) the severity or grade of the adverse event, (4) the phase of the study and attribution (the determination of whether an adverse event is related to a medical treatment or procedure). Any serious adverse event from any cause while a patient is receiving treatment on this protocol or up to 30 days after the last dose of protocol treatment has ended but which is felt to be treatment related must be reported.

12.1 Adverse Event Characteristics

- **CTCAE term (AE description) and grade:** The descriptions and grading scales found in the revised NCI Common Terminology Criteria for Adverse Events (CTCAE) version 4.03 is utilized for AE reporting. All appropriate treatment areas should have access to a copy of the CTCAE version 4.03. A copy of the CTCAE version 4.03 can be downloaded from the CTEP web site (<http://ctep.cancer.gov>).
- **‘Expectedness’:** AEs can be ‘Unexpected’ or ‘Expected’ for expedited reporting purposes only
- **Attribution** of the AE:
 - Definite – The AE is *clearly related* to the study treatment.
 - Probable – The AE is *likely related* to the study treatment.
 - Possible – The AE *may be related* to the study treatment.
 - Unlikely – The AE is *doubtfully related* to the study treatment.
 - Unrelated – The AE is *clearly NOT related* to the study treatment.

12.2 Investigator Reporting: Novartis instructions for rapid notification of serious adverse events

All serious adverse events must be reported to Novartis Pharmaceuticals Drug Safety and Epidemiology Department (DS&E) and reporting will be done via the Investigators or his/her designee.

All events must be reported, by FAX [REDACTED] to Novartis Pharmaceuticals DS&E Department within 24 hours of learning of its occurrence. This includes all serious, related, not related, labeled (expected) and unlabeled (unexpected) adverse experiences.

All deaths during treatment or within 30 days following completion of active protocol therapy must be reported within 24 hours.

Any serious adverse event occurring after the patient has provided informed consent and until 4 weeks after the patient has stopped study participation must be reported. This includes the period in which the study protocol interferes with the standard medical treatment given to a patient (e.g. treatment withdrawal during washout period, change in treatment to a fixed dose of concomitant medication).

Serious adverse events occurring more than 4 weeks after study discontinuation need only be reported if a relationship to the Novartis study drug (or therapy) is suspected.

For Comparator Drugs/Secondary Suspects (Concomitant Medications), all serious adverse experiences will be forwarded to the product manufacturer by the investigator.

Pregnancies

Any pregnancy that occurs during study participation should be reported by the site. To ensure patient safety each pregnancy must also be reported to Novartis within 24 hours of learning of its occurrence. The pregnancy should be followed up to determine outcome, including spontaneous or voluntary termination, details of birth, and the presence or absence of any birth defects, congenital abnormalities or maternal and newborn complications.

Pregnancy should be recorded on a Clinical Study Pregnancy Form and reported by the investigator to the oncology Novartis Drug Safety and Epidemiology (DS&E) department. Pregnancy follow-up should be recorded on the same form and should include an assessment of the possible relationship to the Novartis study treatment of any pregnancy outcome. Any SAE experienced during pregnancy must be reported on the SAE Report Form.

